  - Participants will be encouraged to avoid a large meal before exercise (snack is ok and encouraged). Blood pressure will be monitored before exercise, after the CVEx, and after the REx. As the expected response to exercise would be an increase in blood pressure, the PI will be contacted for any decreases in blood pressure after exercise.
5. **Week 12.**
  - Full physical function, anthropomorphics, questionnaires will be administered on Monday of week 12
  - The **Acute Inflammation visit 2** will occur on Thursday morning of week 12 (**beginning between 7:30-10am**). Arrangements for alternative dates can be made, but the participant must have at least 48 hrs from the prior exercise session). Participants will be encouraged to avoid a large meal before exercise (snack is ok and encouraged). Blood pressure will be monitored before exercise, after the CVEx, and after the REx. As the expected response to exercise would be an increase in blood pressure, the PI will be contacted for any decreases in blood pressure after exercise.
6. **Randomization/Week 13 visit.** At week 13, participants remaining on study will be randomized to either continue moderate intensity or advance to a higher-intensity exercise regimen with the randomization sequence generated by the study statistician ([name]).
  - V02, 1-RM will be measured on Monday of this week to develop a new prescription.
7. **Week 23.**
  - V02, 1-RM will be measured between Wed-Friday of this week.
8. **Week 24.**
  - **Acute inflammation visit 3.** During the week 24 of exercise, participants will be asked to exercise on Monday, Thursday, and Friday.
  - **Thursday (between 7:30-10 am)** will consist of a high intensity CV + REx exercise stimulus, and a blood draw prior to, and 0, 60, and 90 minutes following an exercise stimulus. Participants will be encouraged to avoid a large meal before exercise (snack is ok and encouraged). Blood pressure will be monitored before exercise, after the CVEx, and after the REx. As the expected response to exercise would be an increase in blood pressure, the PI will be contacted for any decreases in blood pressure after exercise.
  - Full physical function testing will occur on the final day of the exercise intervention
9. **Procedure visit #2.** Participants will return >48 hours after the last exercise session for a 2nd procedure visit for muscle biopsy (n=36), DXA scan, and blood draw.
  - DXA
  - Fasting for muscle biopsy (n=36)

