  - Complete questionnaires. If the participant is not part of the muscle biopsy substudy, he/she may complete the procedure visit #2 procedures on the same visit of their final exercise session if preferred.
  - Between consent/baseline visit and procedure visit #1, patients will be sent home with a specimen cup with biosafety bag to collect stool and a 3 day dietary log. The log should be collected in real time during a 3 day time period preceding the procedure visit.
  - Patients will be asked to collect stool within the 72h period prior to procedure visit #2 and place sample in the freezer. They will bring sample to procedure visit and it will be placed immediately in a -80C freezer.
10. **Focus group discussions**
  - Participants agreeing & consenting to participation in this additional part of the study will meet at an agreed upon time in a University of Colorado Hospital conference room for up to 2 hours.
  - Discussion will be audiorecorded.
  - Consent will be obtained prior to beginning focus group discussions

**D. Description, Risks and Justification of Procedures and Data Collection Tools (apply only to the main study participants unless otherwise specified):**

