## **5. Venipuncture:**

Laboratory analyses will include: CBC, CMP at procedure visit #1 only.

HIV antibody for participants that are not known to be HIV+ if no HIV testing available within the past 1 year.

Fasting IGF-I, IGF-BP3, total/free testosterone, IL-6, sTNFRI and sTNFRII, insulin and glucose will be evaluated at procedure visits #1 and #2, and at week 14, at least 48 hours following the last exercise session.

Inflammatory markers (IL-6, sTNFR-1, and TNF-alpha) will be measured pre-exercise, and 0, 60, or 90 minutes, and ~ 24 hours after a high-intensity exercise stimulus at week 2, 12, and 24.

For the optional microbiome substudy, EDTA plasma samples will be assessed for LPS, heparin plasma samples for sCD14, iFABP) and CRP. LPS levels will be measured using the Limulus Amebocyte Lysate (LAL) assay (Lonza, Switzerland) with plasma samples diluted 1:10 in endotoxin free water and heat-inactivated at 80°C for 15min. Commercially available ELISAs will be used to evaluate levels of IL-6, sCD14, and iFABP (all R&D Systems, Minneapolis, MN). Serum LBP levels were assessed using a custom ELISA all as reported in Dillon 2014.

Peripheral blood mononuclear cells (PBMCs) will be collected at each of the pre-exercise acute visits (weeks 2, 12, and 24) and stored. Future analyses (pending funding) will include an assessment of markers of T-cell and B-cell activation

Samples will be stored for additional analyses. These assays will be performed from stored specimens (in batch to minimize inter-assay variability) in the Clinical Translational Research Center (CTRC) core laboratory at UCD or by [name] in [name] laboratory. **All participant samples will be drawn between 7:30-10am. We will draw approximately 70 mL at the initial visit and 75 mL at the subsequent 3 visits.**

Risk: There is a small risk of local hematoma or infection associated with blood sampling.

Plans to minimize risk: The risks of hematoma and infection are minimized by having trained clinical personnel perform the procedures using sterile techniques.

Justification: We will be evaluating the response of HIV+ vs HIV- individuals to an exercise intervention, in hormone levels and markers of inflammation. Additional samples will be collected for storage. These safety and efficacy markers will be imperative in the design of future, larger intervention studies of exercise in HIV.

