Sedentary time and sleep quality will be measured using two tools. Actiwatch Spectrum, accelerometers to collect physical activity and wake/sleep time through additional sensors for light and dark, will be worn for 1 week between the 1st procedure visit and the first exercise visit, and for 1 week between the week 24 and the procedure visit #2.

Accelerometers have been calibrated in [name] laboratory at Rush University, and data will be analyzed in conjunction with her laboratory. We will assess change in sedentary time and change in sleep using the actiwatch. The Pittsburgh sleep index and the Munich Chronotype will assess usual sleep habits and restfulness following sleep.

In addition, each participant will be provided with a pedometer (*Omron Tri-Axis USB Pedometer, HJ-324U*) to wear every day through the study to monitor overall activity patterns and changes with an exercise intervention. This monitor stores 22 days of data. The participant will be asked to bring the monitor every other week and data will be downloaded during the exercise session.

Evaluation of health status, medication use, and falls. A brief health status questionnaire will be completed by participants every 2 weeks to document potential study-related problems/concerns (e.g., exercise discomforts); changes in health status (e.g., hospitalizations), prescription and over-the-counter medications (including non-steroidal anti-inflammatory agents); and falls. The surveys will be reviewed by the study nurse and appropriate follow-up pursued.

Post-intervention follow-up. Participants will be contacted by phone 3 months following study completion. Continued frequency of exercise/physical activity (IPAQ), intent to continue exercising, overall well-being will be assessed.

Risk: A person with a very high depression score may be identified on the CES-D depression screening questionnaire.

Plans to minimize risk: CES-D questionnaires will be briefly reviewed prior to the study participant leaving the visit. If an individual indicates a risk for suicidal ideations or intent on the CES-D, the participant will be referred immediately to their primary care provider or the emergency room.

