Outcome measures will be available bi-weekly for chair rise, and three times for other functional measures. Serum IGF-I, IGFBP3, muscle IGF-1 mRNA/protein, visceral fat, LBM, and inflammatory cytokines will be measured at procedure visits #1 and #2. Secondary outcomes will include change in other cytokines and hormones, sleep quality, quality of life, V02 peak, strength, and modified SPPB. The inflammatory markers will be tested as mediators on the effect of exercise on changes in function and LBM. Additional secondary outcomes will determine if sedentary time increases as the physical activity intensity decreases, the impact of the intervention on the affect and efficacy of exercise. These factors will be important in design of larger interventions and dissemination to identify points of low exercise efficacy and poor affect and attempt to prevent drop-outs from the intervention. An important outcome is to ensure that intensive 3x/week physical activity does not lead to a decrease in usual activity and an increase in sedentary time due to exercise-related fatigue.

For the inflammatory analyses:

**Analysis.** We propose that no subjects in either arm will experience a major injury (e.g., muscle strain or other injury requiring self-prescribed or provider prescribed treatment) and no more than 1 subject in each group will drop out because of exercise-induced discomfort

(i.e., fatigue, muscle or joint pain). The step counts between arms will be compared to determine if the high-intensity group limits non-study activity. For Aim 3, we will compare the change between arms in IL-6, TNF $\alpha$  and sTNFRI (pre-exercise, and 0, 60, and 90 minutes, and 24 hours) with a single bout of exercise at weeks 2, 12, and 24. We also will compare relative changes in serum IL-6, TNF $\alpha$  and sTNFRI from week 2 to week 24 between groups using geometric means and 95% confidence intervals. Secondary outcomes will include the change in other inflammation (sTNFRII, hsCRP, IL-10) and immune activation (sCD14, sCD163) markers, change in physical function, QoL, depressive symptoms, and exercise self-efficacy between study arms. **Sample size and power.** Sample size calculations were conducted for the within and between group percent change in IL-6, TNF $\alpha$ , hs-CRP, and sTNFRI levels. Data from 49 HIV+ subjects with higher function were used to estimate sample size parameters. We anticipate additional power using

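### The option to complete procedure visit #2 at the final exercise session does not exempt the blood draw, contrary to the protocol's own 48-hour sampling condition, and leaves no post-training Actiwatch week

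*Combined protocol and SAP*

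**What the plan says.** **Timing of the visit.** Section C, item 9 (Procedure visit #2) opens: "Participants will return >48 hours after the last exercise session for a" second "procedure visit for muscle biopsy (n=36), DXA scan, and blood draw". A sub-bullet then says of anyone outside the biopsy substudy that "he/she may complete the procedure visit #2 procedures on the same visit of their final exercise session if preferred".

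**Timing of the blood sample.** D.5 Venipuncture lists a fasting panel of IGF-I, IGFBP-3, total/free testosterone, IL-6, sTNFRI, sTNFRII, insulin and glucose, which "will be evaluated at procedure visits #1 and #2, and at week 14, at least 48 hours following the last exercise session". A second set is tied to the acute exercise visits: "Inflammatory markers (IL-6, sTNFR-1, and TNF-alpha) will be measured pre-exercise", then at 0, 60 and 90 minutes and about 24 hours after the stimulus.

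**Week 24 schedule.** Section C, item 8 has participants exercise on Monday, Thursday and Friday. Thursday is the high-intensity acute visit, before which a snack is encouraged.

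**Actiwatch.** D.8 has the end-of-study watch worn "for 1 week between the week 24 and the procedure visit #2"; the first wear week precedes training. It adds: "We will assess change in sedentary time and change in sleep using the actiwatch".

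**Biopsy window.** D.1 Muscle biopsy asks biopsy participants to return within 7 days of the final session.

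**Use of the data.** Section F takes serum IGF-I, IGFBP-3 and inflammatory cytokines from procedure visits #1 and #2. It also treats avoiding a rise in sedentary time as an important outcome.

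**The concern.** A permission in item 9 overrides the interval in that item's opening sentence without saying whether the blood draw goes with it. Site staff could reasonably draw the end-of-study panel on an exercise day. The visit #1 sample is taken before training, so any acute effect of exercise would enter only the follow-up half of each change score. It would do so only for participants who were not biopsied and who chose the option. Sampling time would then depend on biopsy status and personal preference, and the plan does not call for it to be recorded.

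The outcomes at stake are the serum change measures in section F. Hypothesis 2a on systemic IGF-I is also involved if its week 20 stands for the end-of-study sample; the hypothesis names week 20, not procedure visit #2.

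The Actiwatch has a parallel problem. If visit #2 coincides with the last session, there is no interval in which to wear the watch after training, so the second week is either missing or falls inside a training week.

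**Working it through.** **1. The timing rules side by side**

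| Source | Gap between last session and visit #2 draw |
|---|---|
| C, item 9, opening sentence | more than 48 h |
| C, item 9, same-day option | 0 h; no procedure excepted |
| D.5, fasting panel | at least 48 h, if the clause covers visit #2 as well as week 14 |

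**2. Would drawing before the session help?** If the final session is the Friday of week 24, a draw taken first is still only about 24 h after Thursday's high-intensity bout. Section F itself treats that interval as part of the acute response, comparing markers "pre-exercise, and 0, 60, and 90 minutes, and 24 hours) with a single bout of exercise at weeks 2, 12, and 24". So the possible range is 0 to about 24 h.

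**3. How many participants?** Inputs: 36 per group enrolled and 29 per group expected after dropout (section F, stated for week 16); 36 biopsied, up to 46 (section C, item 2).
- Expected completers: 2 × 29 = 58. Check against the 80% completion in Hypothesis 1c: 0.80 × 72 = 57.6.
- Eligible with 36 biopsied: 58 − 36 = 22, and 22/58 = 38%.
- Eligible if 46 are biopsied and all complete: 58 − 46 = 12, and 12/58 = 21%.
- Floor: 0, if nobody uses the option or D.5 is taken to govern.

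**4. Is there another rested week 24 sample?** Monday to Thursday of week 24 is about 72 h, so Thursday's pre-exercise draw is rested. D.5 lists IL-6, sTNFRI and TNF-alpha there. Counting total/free testosterone once, the fasting panel has 8 analytes, of which 2 (IL-6 and sTNFRI) overlap, leaving 8 − 2 = 6. Five of these are firm: IGF-I, IGFBP-3, testosterone, insulin and glucose. The sixth, sTNFRII, is less so, because section F lists its change among the secondary outcomes of the inflammatory analysis. The Thursday draw is not fasting in any case. The week 14 panel comes about one week after randomization and cannot stand for the 24-week value.

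**5. Actiwatch.** Required: 7 days. With a same-day visit, 0 days remain after the last session. Counting from Monday of week 24 to a Friday visit gives about 4 days, all in training. The permitted extension of up to 4 weeks would add training time, not a post-training week. The window is also tight for biopsy participants: more than 48 h (item 9) and within 7 days (D.1) together admit a full week only at about day 7.

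**6. Precision of a sensitivity analysis without draws under 48 h.** Two-sample t-test by HIV status, two-sided 0.05, 80% power, exclusions split evenly between groups:

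| Excluded | n per group | Detectable difference |
|---|---|---|
| 0 | 29 | 0.749 SD |
| 12 | 23 | 0.845 SD |
| 22 | 18 | 0.961 SD |

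These figures describe only that added analysis. The plan sets no power target for serum IGF-I, so they show no loss in the existing plan.

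**The case against.** The strongest reply is that D.5 is the specific rule for this sample and most naturally covers visit #2. If staff follow it, every draw is rested and no sample is affected. The same-day sentence can also be read as a deliberate exception for convenience. It follows the questionnaires bullet, and the item's sub-bullets name DXA, biopsy fasting and questionnaires; only the opening sentence mentions blood. Much of this stands: the harm is conditional on which text is followed. But on this reading D.5 and the same-day option contradict each other, and nothing says which prevails. If the 48-hour clause is attached to week 14 alone, exercise-day draws are simply allowed. The text needs reconciling either way.

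It is also fair that the option is voluntary, that its text never mentions the Actiwatch, and that IPAQ and pedometer data remain. Loss of the watch week is an inference, but it follows because no interval is left. D.8 gives the change in sedentary time and sleep to this device.

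A reader might infer that the plan biases serum IGF-I change, or the HIV comparison. The documents do not support that. They give neither uptake nor an acute effect for IGF-I, and the Background calls exercise-related changes in systemic IGF-I inconsistent. Biopsies are planned 18 and 18 by HIV status, so that comparison would be distorted only if uptake or acute response differed by group. Hypotheses 3a and 3b anticipate differing acute cytokine responses, which makes this possible but does not demonstrate it.

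**Conclusion.** The point holds as an internal contradiction with a limited consequence. Followed as written, the same-day option lets up to 22 of about 58 completers (12 if all 46 biopsied complete; floor 0) give the end-of-study fasting panel 0 to about 24 h after exercise, to be pooled with rested samples. It also leaves those participants without a post-training Actiwatch week. The counts are ceilings on eligibility, not estimates of use. They assume that the dropout stated for week 16 carries to the end and that the biopsied all complete.

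The loss is in comparable sampling conditions for the serum and actigraphy change outcomes. No bias in either direction can be computed. Rested week 24 IL-6, TNF-alpha and sTNFRI are available from the Thursday draw; D.5 schedules no other rested week 24 IGF-I or IGFBP-3. Chair rise and muscle IGF-I mRNA, the two outcomes named primary, are unaffected. Severity is minor to moderate.

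**What to change.** Reconcile section C, item 9 with D.1, D.5 and D.8:

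- Limit the same-day option to DXA and questionnaires. Apply the protocol's own 48-hour and fasting conditions to the visit #2 blood draw for all participants.
- State when the end-of-study Actiwatch week falls for all participants, including biopsy participants with the 7-day limit. For users of the same-day option, the watch can be returned at the blood visit.
- Record hours since last exercise and fasting status with every draw.
- If a participant will not return, keep the same-day sample and flag it. Repeat the serum change analyses without draws under 48 h as a sensitivity analysis.

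The cost is one short fasting return visit for those who would have used the option (0 to 22 of 58), two data fields and a few protocol sentences. Some participants may miss the extra visit; keeping the flagged sample limits that loss.

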## C. Study Design and Research Methods

Potentially eligible subjects will be screened during routine clinic visits or over the telephone. Potentially eligible and interested subjects will return for informed consent and a screening/baseline visit. No research procedures will occur prior to consent, including the MOCA.

After obtaining informed consent, participants will undergo a graded exercise test to screen for potential underlying cardiovascular disease. V02 peak will be measured at this time to develop the exercise prescription. All participants will begin with a low intensity lead-in for 1-2 weeks, then advance to a moderate intensity exercise during first 12 weeks. Randomization to continue on moderate versus advance to high intensity will occur at week 13.

**1. Consent & baseline visit.** After obtaining consent, the participant will be evaluated

-After obtaining consent, the participant will be evaluated by

- medical history, physical examination including vital signs
- Montreal Cognitive Assessment (MOCA)
- Resting BP, 12-lead resting ECG, and then a graded exercise test (GXT) administered by research personnel and a clinician experienced in exercise stress testing of older adults ([name]) to screen out volunteers with evidence of ischemic heart disease, serious arrhythmias, or abnormal HR/BP responses to exercise. Briefly, the test will begin at a comfortable walking speed and 0% elevation; speed will be maintained and the grade increased by 2% every 2 min, until the participant reaches 85% of age-predicted maximal heart rate or the test is otherwise terminated. The absolute and relative indicators for terminating an exercise test that are recommended by the American College of Sports Medicine (ACSM) will be employed.
- Baseline physical function assessments will be administered.

**2. Procedure visit #1 (within 14 days of visit #1).** All participants will arrive between 7:30-8am for:

- DXA scan
- Vital signs
- Anthropometrics (waist/hip circumference)
- Blood draw (fasting)
- 36 (up to 46, if needed to ensure 36 paired biopsy samples) volunteer participants (18 HIV+/18 HIV-) will have a muscle biopsy
  - If muscle biopsy at the end of the study cannot be done (patient refuses, change in medications, etc), then the number of biopsies will increase to a maximum of 46 in order to ensure each group has at least 18 paired (entry/completion) biopsy samples.
- Questionnaires

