- Between the procedure #1 visit and the first exercise visit, participants will be sent home with an ActiWatch Spectrum monitor for activity and sleep.
- Between consent/baseline visit and procedure visit #1, patients will be sent home with a specimen cup with biosafety bag to collect stool and a 3 day dietary log. The log should be collected in real time during a 3 day time period preceding the procedure visit.
- Participants will be asked to collect stool within 72h period (if possible) prior to procedure visit #1 and place sample in a biosafety bag in their home freezer. They will bring the sample to procedure visit and it will be placed immediately in a -80C freezer within the RC2 11th floor lab.

**3. Exercise training.** The exercise intervention will begin at least 24 hours following, and within 14 days of the procedure visit (+/- 14 days for illness, scheduled vacation, etc).

- At the first visit, all participants will repeat physical function testing & 1-RM
- The first 2 weeks will be a lead-in period with low intensity exercise to gain familiarity with the machines. He/she will then be advanced to a moderate intensity exercise for an additional 10 weeks.
- During the exercise training, participants will come to the research center 3 to 4 days/week.
- Chair rise will be measured at the first visit of the week, every 2 weeks and pedometer data will be downloaded.
- To account for unforeseen absences from exercise (due to death of family/friends, illness, etc), the duration of exercise can be extended by up to 4 weeks. This will allow the participant to slowly acclimate back to the prior exercise intensity and minimize risk for injury. The exercise will only be extended if the participant is in agreement. If he/she wishes to complete the exercise intervention within the 24 weeks as planned, then the duration will not be extended.

4. **Acute inflammation visit 1.** At 3 time points during the study, participants will have an “acute exercise visit”.
  - The first will occur during week two of exercise
  - Participants will be asked to exercise on Monday, Thursday, and Friday.
  - **Thursday (beginning between 7:30-10am)** will consist of a high intensity CV + REx exercise stimulus, and a blood draw prior to exercise, and 0, 60, and 90 minutes following an exercise stimulus.

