**1. Muscle biopsy.** Subjects participating in the muscle biopsy portion will have a biopsy prior to beginning the exercise intervention and after completing the 24 week intervention. Subjects will be advised to refrain from any physical activity for at least 48 hours following the biopsy and return within 14 days of the screening/consent visit. Non-steroidal anti-inflammatories or aspirin are held for 7 days prior to the biopsy. If participants are taking direct oral anticoagulants, this will be held for 48 hours prior to the procedure (72 hours if creatinine clearance is 30-50 and taking dabigatran). Therapy can be resumed 24 hours after the procedure, or as instructed by their physician. At study completion, subjects will be asked to return within 7 days of the final exercise session for a muscle biopsy. The exercise intervention will begin >24 hours after the initial biopsy, but within 14 days. Participants will be asked to abstain from alcohol or caffeinated beverages after 1300h and to fast from any food or drink beginning at 9pm with the exception of water. Subjects will arrive at 8am in the CTRC for the biopsy. Percutaneous samples of the vastus lateralis muscle will be obtained. After cleansing the area of the thigh with antiseptic (e.g., chlorhexidine, Betadine solution), 1% lidocaine (without epinephrine) will be injected under the skin. A 3-5 mm incision will be made in the skin and fascia over the belly of the vastus lateralis, and 100-150 mg of muscle tissue will be removed using a Bergstrom side-cutting biopsy needle with suction applied. The incision will be closed and a compression wrap and ice will be applied to the incision area for 20 minutes. The patient will be given instructions for wound care before discharge.

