**Muscle protein expression.** The protein expression of IGF-1, IGF receptor, IL-6R, SOCS-3, TNFα, TNFR-1, NF-*κB* and MuRF1; *PGC1-α* and Mitochondrial Transcription Factor (mt biogenesis), citrate synthase (mt function); *Mfn-1* and -2, *Opa1*, *FIS-1* and *Drp1* (mt fusion/fission) will be measured by established Western Blot techniques[139] using commercially available antibodies (Cell Signaling Technology, Inc., Beverly, MA).

**Risks:** The risks associated with muscle biopsy include brief, mild burning pain from the local anesthetic (lidocaine), more than mild discomfort during the acquisition of tissue (about 10% of cases), and infection (less than 0.4% of cases). Allergy to the anesthetic (skin swelling or rash) occurs rarely. There may be persistent numbness in the biopsy area.

**Plan to Minimize Risk:** Risks of the muscle biopsy procedure will be *minimized* by having a trained clinician perform the procedure on participants who meet the biopsy-specific criteria listed above. As part of her career development award, [name] is obtaining the skills in muscle biopsy. She is currently being trained in the procedures and will not begin performing the biopsies until her skills have been approved by an experienced clinician ([name] and/or [name]) with expertise in muscle biopsies. Participants will be observed following the procedure for any adverse events and given strict instructions for wound care. A phone call will be made within 48 h of the biopsy procedure to assess wound healing with a study clinician. Only non-diabetics participants and participants with a CD4 count >200 cells/mm^3 will be eligible to participate which will further minimize risk for post-biopsy infection. Additionally, the study will have a safety officer ([name], a physician in the Infectious Diseases clinic). [name] will review

biopsy and exercise safety with [name] every 6 months.

Justification: Systemic IGF-I does not appear to be nearly as strongly linked to muscle adaption to exercise as local IGF-I at the level of the muscle. Additionally, skeletal muscle mitochondria are reflective of insults that may have occurred decades earlier, whereas mitochondrial studies obtained through peripheral blood would only reflect changes over a much shorter time period. Thus the muscle specimens provide a window into mechanisms well beyond what can be collected less invasively.

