*Muscle strength (1-RM).* Muscle strength will be evaluated as the 1-RM (the maximal weight that can be lifted only 1 time using correct lifting form through the full range of motion) for the upper and lower body REx performed during weeks 1-20. 1RMs will be measured at week 0 and every 4 weeks to week 20. The change in muscle strength from week 0 to 20 will be a secondary outcome measure.

*Exercise intervention.* CEx duration will be increased to 50 minutes of treadmill walking/jogging and exercise intensity will be gradually increased to either 40-50% VO2max (moderate intensity) or 60-70% VO2max (high intensity). By completing 50 minutes of CEx within the 3 weekly visits, we will ensure that all subjects comply with the DHHS guidelines, regardless of their physical activity outside of the routine visits. REx intensity will increase every 2-3 weeks to a target of 3 sets of 8 repetitions at 60-70% of 1-RM (moderate intensity) or >80% of the 1-RM (high intensity).

*Supervised exercise sessions.* Each session will begin with CEx and proceed to REx. Three sets of resistance exercises will include leg press, knee extension, knee flexion, lunges (forward and side), lateral pulldown, chest press, seated row, and dips on a weight-assisted machine. Weight-stack and free weight equipment will be used. Stretching for 10 minutes will conclude each session. Research assistants will supervise exercise, interact frequently with participants, and encourage feedback regarding any discomforts or undue fatigue experienced during or after the exercise sessions. The individualized exercise prescriptions will be geared toward increasing the exercise stimulus while avoiding unfavorable events.

*Physical activity recommendations outside of supervised sessions.* Each participant will be provided with a pedometer (Omron) and recommendations to achieve at least 5,000 steps/day. Walking paths near the participants' home will be mapped for each participant. Information from the NIH Healthy Aging site (exercises for the older adults, nutrition advice, etc) will be provided to each participant at study entry and tip sheets for ways to decrease sedentary time will be provided. Participants will be encouraged to utilize fitness apps (MyFitnessPal, etc) and each subject will receive instructions to partake in physical activity "most" days of the week, outside of their 3x/week supervised sessions.

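### Biopsied participants are advised to rest for at least 48 hours, but the plan lets exercise, with a maximal strength test at the first visit, start after 24 hours

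*Combined protocol and SAP*

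**What the plan says.** Four parts of the protocol bear on this point.

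- **Rest after biopsy (IV.D, item 1, Muscle biopsy).** The sample is taken from the vastus lateralis through an incision in skin and fascia. The advice is: "Subjects will be advised to refrain from any physical activity for at least 48 hours following the biopsy". Under the plan to minimize risk: "A phone call will be made within 48 h of the biopsy procedure to assess wound healing with a study clinician".
- **Start of exercise.** The same item says: "The exercise intervention will begin >24 hours after the initial biopsy, but within 14 days". Section IV.C, item 3 (Exercise training) says: "The exercise intervention will begin at least 24 hours following, and within 14 days of the procedure visit". That second rule applies to everyone, with no longer minimum for the biopsy subset.
- **Content of the first exercise visit (IV.C, item 3).** "At the first visit, all participants will repeat physical function testing & 1-RM". Section IV.D, item 2 defines the 1-RM as a maximal single lift, covering upper- and lower-body exercises. On its use as an outcome: "The change in muscle strength from week 0 to 20 will be a secondary outcome measure".
- **Other scheduling.** Section IV.D, item 8 says the Actiwatch "will be worn for 1 week between the 1st procedure visit and the first exercise visit". At the consent visit, before any biopsy (IV.C, item 1): "Baseline physical function assessments will be administered".

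**The concern.** The rest advice and the start rule sit in one paragraph and give different minimum intervals after the same procedure. Staff book visits from the written minimum, and here that is the less protective figure. Someone told to rest for two days could be booked the next day for a maximal leg test on the biopsied thigh.

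The low-intensity lead-in does not resolve this. The advice covers all physical activity, and the 1-RM at the first visit is a maximal effort by definition. A visit at 24 to 48 hours may also come before the wound-healing call, which can be made at any time up to 48 hours.

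Participant protection is the main stake. Measurement is secondary: the first-visit 1-RM is the only pre-training 1-RM in the visit schedule, so it is the starting point for the strength outcome and the basis for the lead-in resistance loads. A sore thigh could lower it.

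**Working it through.** The plan states no figure to reproduce, so the check compares its time limits and asks who falls between them.

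**Inputs**

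| Item | Value | Source |
|---|---|---|
| Rest advised after biopsy | at least 48 h | IV.D, item 1 |
| Earliest exercise start | 24 h | IV.D, item 1; IV.C, item 3 |
| Latest exercise start | 14 days | IV.D, item 1; IV.C, item 3 |
| Biopsied participants | 36, up to 46 | IV.C, item 2 |
| Total sample | 72 (36 HIV+, 36 HIV-) | Specific Aim 1; IV.F |
| Actiwatch wear before first exercise visit | 1 week | IV.D, item 8 |

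**Step 1. Width of the conflict.** 48 - 24 = 24 h. A first visit in this interval meets the start rule and breaches the rest advice. At 48 h or later, both are met.

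**Step 2. Who is covered.** 36/72 = 50%; at the maximum, 46/72 = 64%. These count the participants to whom the two rules apply, not those expected to start early.

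**Step 3. What a 48-hour minimum removes.** 14 days = 336 h. The permitted window is now 336 - 24 = 312 h and would become 336 - 48 = 288 h. The loss is 24/312 = 7.7%. IV.C, item 3 also allows 14 days either way for illness or vacation. If that extends the limit to 28 days (672 h), the loss is 24/(672 - 24) = 24/648 = 3.7%.

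**Step 4. Effect of the monitor week.** One week = 168 h, later than both 24 h and 48 h. If the wear is completed as planned, no start falls in the conflicting interval and the fix removes no usable time.

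**Step 5. Effect on outcomes.** The documents give nothing from which to estimate how a recent biopsy changes a 1-RM or chair-rise time, so no estimate is made. Chair rise could be affected only if week 0 means the first exercise visit, because function is also tested at consent. Biopsies are planned equally, 18 HIV+ and 18 HIV-, so any effect would fall on both groups.

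**The case against.** The strongest reply is that the text permits a breach without requiring one, and that other procedures leave the interval almost empty.

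- **Both rules can be met by waiting.** True. The fault is that the minimum is too low for these participants.
- **The Actiwatch week makes a next-day start unlikely.** This stands, and it limits the practical consequence. But it is a monitoring instruction. The start rule is stated separately, twice, as 24 hours, and IV.C, item 3 allows that start immediately after a mention of the Actiwatch that gives no one-week duration.
- **Strength testing has its own safeguards.** Section IV.D, item 2 calls for technique instruction on several days before testing, gradual loading and warm-up, with a physician's written orders on whether a clinician must attend. These reduce the risk. However, the visit schedule shows no instruction days before the first exercise visit and places the 1-RM at that visit.
- **The wound call may come first.** Correct: a call due within 48 hours could precede a visit at 24 to 48 hours. Only the possibility of the reverse order is claimed.
- **The percentages do not measure harm.** Also correct. The 50% and 64% describe coverage, and the 7.7% or 3.7% describes the cost of the fix.
- **A 48-hour minimum still differs from the one-week wear.** True, but that mismatch concerns completeness of the baseline activity record, not the rest advice.

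**Conclusion.** The concern holds. The plan's start rule allows biopsied participants to begin exercise, including a maximal lower-body strength test, up to 24 hours before the rest period it advises has ended. It covers 36 participants, up to 46. The number actually exposed is probably small, and would be none if the one-week monitor wear is completed every time.

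This is a safety and scheduling inconsistency that should be corrected. It does not affect the sample size and does not materially bias the HIV+ versus HIV- comparison. Any effect on the pre-training 1-RM is confined to early starters and cannot be sized from the documents. The conclusion assumes only that staff may schedule by the written 24-hour minimum.

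**What to change.** Set a 48-hour minimum for biopsied participants in both places and keep the 14-day limit.

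- **IV.D, item 1:** replace the start sentence with wording such as *After a muscle biopsy, no function test, 1-RM test or training session takes place until at least 48 hours have passed; the first exercise visit follows within 14 days.*
- **IV.C, item 3:** after the 24-hour minimum, add *(48 hours or more if a muscle biopsy was done)*.

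Forty-eight hours is the protocol's own figure and the shortest minimum consistent with both current statements. The wound-healing call would then be due before the first exercise visit. If the Actiwatch week is meant to be mandatory, the sponsor could also state it in IV.C, item 3.

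The cost is one line in each of two sections and at most a one-day later start for biopsied participants, usually none given the monitor week. Nothing changes for participants without a biopsy.
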